13.5 Changes in the Conduct of the Study or Planned Analyses

Any change in study conduct considered necessary by the Investigator will be made only after consultation with Catalyst, who will then issue a formal protocol amendment to implement the change. The only exception is when an Investigator considers that a patient's safety is compromised without immediate action. In these circumstances, immediate approval of the IRB/IEC/REB must be sought, and the Investigator should inform Catalyst within 2 working days after the emergency occurs.

Page 55

14 COMPENSATION, INSURANCE AND INDEMNITY

There will be no charge to study patients to be in this study. Catalyst will pay all costs of test, procedures, and treatment that are part of this study (as included in the site budget). In addition, after IRB/IEC/REB approval, Catalyst will pay the cost of travel, lodging and meals for study duration. Catalyst will not pay for any hospitalizations, tests, or treatment for medical problems of any sort, whether or not related to the study patient's disease that are not part of this study. Costs associated with hospitalizations, test, and treatments should be billed and collected in the way that such costs are usually billed and collected.

The Investigator should contact Catalyst immediately upon notification that a study patient has been injured by the IP or by procedures performed as part of the study. Any patient who experiences a study-related injury should be instructed by the Investigator to seek medical treatment at the closest medical treatment facility if necessary. The patient should be given the name of a person to contact to seek further information about, and assistance with, treatment for study-related injuries. The treating physician should bill the patient's health insurance company or other third party payer for the cost of this medical treatment. To the extent a patient has reasonably followed the Investigator's instructions and attempted to comply with study procedures, Catalyst will pay for reasonable and necessary medical services to treat the injuries caused by the IP or study procedures, if these costs are not covered by health insurance or another third party that usually pays these costs. In some jurisdictions, Catalyst is obligated by law to pay for study-related injuries without prior recourse to third party payer billing. If this is the case, Catalyst will comply with the law.

15 CASE REPORT FORMS AND SOURCE DOCUMENTS

The CRO data management vendor, or designees, will perform all data management activities, including the writing of a data management plan outlining the systems and procedures to be used.

Study data will be captured on CRFs and will be verified to the source data, which necessitates access to all original recordings, laboratory reports, and patient records. In addition, all source data should be attributable (signed and dated). The Investigator must therefore agree to allow direct access to all source data. Patients must also allow access to their medical records, and patients will be informed of this and will confirm their agreement when giving informed

Page 56

consent. The Investigator must review and sign the completed CRF casebook to verify its accuracy.

16 STUDY MONITORING AND AUDITING

Qualified individuals approved and/or designated by Catalyst will monitor all aspects of the study according to GCP and SOPs for compliance with applicable government regulations. The Investigator agrees to allow these monitors direct access to the clinical supplies, dispensing, and storage areas and to the clinical files, including original medical records, of the study patients, and, if requested, agrees to assist the monitors. The Investigator and staff are responsible for being present or available for consultation during routinely scheduled site visits conducted by Catalyst or its designees.

Members of Catalyst's GCP Compliance Department or designees may conduct an audit of a clinical site at any time before, during, or after completion of the study. The Investigator will be informed if an audit is to take place and advised as to the scope of the audit. Representatives of the FDA or other regulatory agencies may also conduct an audit of the study. If informed of such an inspection, the Investigator should notify Catalyst immediately. The Investigator will ensure that the auditors have access to the clinical supplies, study site facilities, original source documentation, and all study files.

17 RETENTION OF RECORDS

The Investigator must retain all study records required by Catalyst and by the applicable regulations in a secure and safe facility. The Investigator must consult a Catalyst representative before disposal of any study records, and must notify Catalyst of any change in the location, disposition or custody of the study files. The Investigator/institution must take measures to prevent accidental or premature destruction of essential documents, that is, documents that individually and collectively permit evaluation of the conduct of a study and the quality of the data produced, including paper copies of study records (e.g. patient charts) as well as any original source documents that are electronic as required by applicable regulatory requirements.

All study records must be retained for at least 2 years after the last approval of a marketing application in an ICH region and until (1) there are no pending or contemplated marketing applications in an ICH region or (2) at least 2 years have elapsed since the formal

Page 57

discontinuation of clinical development of the IP. The Investigator/institution should retain patient identifiers for at least 15 years after the completion or discontinuation of the study. Patient files and other source data must be kept for the maximum period of time permitted by the hospital, institution or private practice, but not less than 15 years. These documents should be retained for a longer period, however, if required by the applicable regulatory requirements or by a Catalyst agreement. Catalyst must be notified and will assist with retention should Investigator/institution be unable to continue maintenance of patient files for the full 15 years. It is the responsibility of Catalyst to inform the Investigator /institution as to when these documents no longer need to be retained.

18 USE OF INFORMATION AND PUBLICATION

Catalyst recognizes the importance of communicating medical study data and therefore encourages their publication in reputable scientific journals and at seminars or conferences. The details of the processes of producing and reviewing reports, manuscripts, and presentations based on the data from this study will be described in any Clinical Trial Agreement.

Page 58

Appendix 1 Quantitative Myasthenia Gravis Testing Form

TEST ITEMS WEAKNESS	NONE	MILD	MODERATE	SEVERE	SCORE
GRADE	0	1	2	3	
Double vision (lateral gaze) Sec.	60	11-59	1-10	Spontaneous	
Ptosis (upward gaze) Sec.	60	11-59	1-10	Spontaneous	
Facial Muscles	Norma llid closure	Complete, weak, some	Complete, without resistance	Incomplete	
Swallowing 4 oz. Water (1/2 cup)	Normal	Minimal coughing or throat clearing	Severe coughing Choking or nasal regurgitation	Cannot swallow (test not attempted)	
Speech following counting aloud from 1-50 (onset of dysarthria)	None at #50	Dysarthria at #30-49	Dysarthria at #10-29	Dysarthria at #9	
Right arm outstretched (90°, sitting) Sec.	240	90-239	10-89	0-9	
Left arm outstretched (90°, sitting) Sec.	240	90-239	10-89	0-9	
Forced vital capacity	≥80%	65-79%	50-64%	<50%	
Rt hand grip: male (Kg) :	≥45 ≥30	15-44 10-29	5-14 5-9	0-4 0-4	
Left hand grip: male (Kg) :	≥35 ≥25	15-34 10-24	5-14 5-9	0-4 0-4	
Head, lifted (45%, supine) Sec.	120	30-119	1-29	0	
Right leg outstretched (45-50%, supine) Sec.	100	31-99	1-30	0	
Left leg outstretched (45-50%, supine) Sec.	100	31-99	1-30	0	

Page 65

Appendix 2 Subject Global Impression (SGI)

The SGI will be assessed at the protocol-specified time points (see Table 3) by the patient.

Using the 7-point scale below, rate your impression of the effects of the study medication during the preceding 3 days on your physical well being.

- 1=Terrible
- 2= Mostly dissatisfied
- 3= Mixed
- 4=Partially satisfied
- 5= Mostly satisfied
- 6= Pleased
- 7= Delighted

Page 66

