8.1 Overall Study Design and Plan

This randomized (1:1), double-blind, placebo-controlled, parallel-group study is designed to evaluate the efficacy and safety of amifampridine phosphate in patients diagnosed with LEMS. Patients will have been receiving unblinded drug treatment in the expanded access program (EAP-001), after which blinded treatment effect will be assessed for continuation or cessation of drug. The study is planned to include approximately 28 male and female patients. The planned duration of participation for each patient is 5 days, excluding the screening period, which can last up to 7 days.

Those patients successfully satisfying all screening criteria will be randomized to a treatment group. Amifampridine phosphate (at the patient's optimal dose) or placebo will be dispensed by the site pharmacist, according to the randomization schedule, to begin with the next dose after all Day 0 assessments are completed and continued for 4 days. After completion of the study, patients will be eligible for expanded access treatment program with open-label amifampridine phosphate. Since patients will have been out of the expanded accesss program for less than 30 days, as LMS-003 participants, rescreening to return to expanded access program will not be required, per the protocol, and patients may immediately resume their participation in the expanded access program (EAP-001).

Page 29

Screening

Patients receiving amifampridine phosphate treatment for LEMS, and meeting the inclusion and exclusion criteria are eligible to participate in this study. They can be randomized if on stable dose and frequency of amifampridine phosphate for at least 1 week before being randomized to a treatment. Screening and randomization (Day 0) may be combined into a single visit.

Treatment (Days 1-4) (+1 day)

Patients will be randomized (1:1 ratio) on the last day of the screening period (Day 0) to either amifampridine phosphate or placebo. Beginning with the next dose after all Day 0 assessments are completed, the patient will take, under double-blind conditions, either amifampridine phosphate tablets or placebo tablets through Day 4, with a clinic visit on the last day (Day 4) for assessments (Table 3). Any unused portion of dispensed drug will be returned to the pharmacy.

During the study, safety and efficacy assessments will be made as detailed in the Schedule of Assessments in Table 3.

Table 3. Schedule of Assessments

	Samaaning	Randomization	Days 1-4

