8.2.1 Inclusion Criteria

Individuals eligible to participate in this study must meet all of the following inclusion criteria:

- 1. Male or female ≥18 years of agewith LEMS and currently receiving a stable dose of amifampridine phosphate for at least 7 days.
- 2. Diagnosis of LEMS by antibody testing or EMG.
- 3. Completion of anti-cancer treatment at least 3 months (90 days) prior to Screening.
- 4. If receiving peripherally acting cholinesterase inhibitors (e.g. pyridostigmine), a stable dose of cholinesterase inhibitors is required for at least 7 days prior to randomization and throughout the study.
- 5. If receiving permitted oral immunosuppressants (prednisone or other corticosteroid,), a stable dose is required for at least 30 days prior to randomization and throughout the study.
- 6. Female patients of childbearing potential must practice effective, reliable contraceptive regimen during the study.
- 7. Able to perform all study procedures and assessments.
- 8. Willing and able to travel to study site and attend all clinic study visits.
- 9. Willing and able to provide written informed consent.

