8.7.1 Subject Global Impression

The SGI (Farrar, 2001) is a 7-point scale on which the patient rates their global impression of the effects of a study treatment (1 = terrible to 7 = delighted). The SGI will be assessed by the patient or the patient's parent/guardian/caregiver if the patient is unable to complete the SGI.

[°]Except on Day 0

Page 41

The SGI has demonstrated concordance with the physician's assessment of improvement (Dodick, 2007). Instructions for the SGI are provided in Appendix 2 and the LMS-003 Study Reference Manual.

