11.2 Randomization Visit (Study Day 0)

The study activities listed below will be performed on Study Day 0, while the patient has been on open-label amifampridine phosphate and in relationship to the usual dosing schedule.

Assessment	Start Time After Dose* (+ 10 minutes unless otherwise specified)
SGI	40 minutes
Patient most bothersome symptom, Question 1	Following SGI
QMG	Following patient symptom evaluation
3TUG	Following QMG

^{*}Administration of medication represents Time 0 (minutes)

- Assessment of AEs/SAEs
- Assessment of concomitant medications

Patients who are deemed eligible will be dispensed double-blind study medication (amifampridine phosphate or placebo tablets) on Study Day 0, according to the treatment group to which they are randomized. The patient's open-label amifampridine must be collected. Patients must stop their open-label amifampridine and will start to take the blinded study

Page 50

medication beginning with the next scheduled dose after all assessments on open-label medication have been completed.

Patients must be instructed that they are not to take any doses of their prior, open-label amifampridine during the study and not to change pyridostigmine dose or schedule.

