11.4 Early Discontinuation Visit

Any patient that discontinues from the study, regardless of the reason, will be requested to complete all Early Discontinuation visit assessments/procedures as listed below after the last dose of study medication. Every reasonable effort should be made to contact any patient who is lost to follow-up.

In cases of Early Discontinuation, medication will have been stopped some time prior to seeing the patient for the below assessments. The date and time of the last dose of medication should be recorded in relation to when the assessments are performed.

- Assessment of AEs/SAEs
- Vital signs
- Concomitant medications
- IP accountability
- SGI
- CGI-I (compared to Day 0)
- Patient most bothersome symptom, Question 2
- QMG
- 3TUG

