Appendix 5 Most Bothersome Symptom Scale

Question 1:

Before treatment for LEMS or while off of medication, what was your most bothersome symptom and how would you rate it?

- 0 = Not at all bothersome
- 1 = Bothered me a little
- 2 = Bothered me some
- 3 = Bothered me a lot

Question 2:

After treatment with the study medication, how would you rate the most bothersome symptom that you previously identified, during the last 24 hours?

- 0 = Not at all bothersome
- 1 = Bothers me a little
- 2 = Bothers me some
- 3 = Bothers me a lot

Page 70

Appendix 6 Protocol Amendment 1

PURPOSE: The purpose of this amendment is as follows:

Risk: these administrative changes provide clarity, adding no additional risk to the patient.

MODIFICATIONS TO PROTOCOL:

Bold and underlined text: Changed Text
 Bold and strike through text: Deleted Text
 Bold and italicized text: Added Text

On Page 1, on the header changed text.

Amendment 1

On Page 1, under Study Title, deleted and added text.

Two period Two treatment Crossover

Parrallel- Group

On Page 1, under Study Design, deleted and added text.

Two period Two treatment Crossover

Parrallel- Group

On Page 1, under Date of Protocol added text.

Date of Amendment 1: 18 September 2016

On Page 3, under Title of Study, deleted text and added text.

Two period Two treatment Crossover

Parrallel- Group

On Page 3, under Study Design and Plan, deleted and added text.

Two period Two treatment Crossover

Parrallel- Group

On Page 3, under Study Design and Plan, deleted up to 24 males and added added 28.

The study is planned to include up to 24 approximately 28 male and female patients.

On Page 3, under Study Design and Plan, deleted 8 days and added 5 days (Day 0 through Day 4).

Page 71

The planned duration of participation for each patient is 8 5 days (Day 0 through Day 4), excluding the screening period, which can last up to 7 days.

On Page 4, under Study Design and Plan, deleted and added text.

Treatment Sequence Group.

On Page 4, under Study Design and Plan, deleted and added text.

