2.3 Missing Data Conventions

No missing value imputation will be used in this analysis. All analyses will be based on the observed data. For subjects that discontinue prior to Day 4 due to treatment related disability ("Rescue"), the observations collected at the time of rescue will be analyzed with the other Day 4 observations.

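### At an Early Discontinuation visit less than 72 hours after the switch to blinded tablets, the SGI's fixed 3-day window reaches back into open-label treatment, yet the score is analysed with Day 4

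*Protocol*

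**What the plan says.** Protocol 8.7.1 describes the SGI as a 7-point scale on which "the patient rates their global impression of the effects of a study treatment", and gives no recall period. Appendix 2 supplies it: "rate your impression of the effects of the study medication during the preceding 3 days on your physical well being". SAP Data Listing 12 carries the same 3-day label. Table 3 and section 11.4 use the item on Day 0, on Day 4 and at Early Discontinuation, with no separate version for any of them.

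Patients enter while "currently receiving a stable dose of amifampridine phosphate for at least 7 days" (Protocol 8.2.1). The Day 0 ratings are made "while the patient has been on open-label amifampridine phosphate and in relationship to the usual dosing schedule" (11.2). Blinded tablets are dispensed "to begin with the next dose after all Day 0 assessments are completed and continued for 4 days" (8.1).

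Protocol 8.2.3 lets a patient whose LEMS worsens to a clinically significant level move to open-label drug and then have the Early Discontinuation assessments. It names no earliest day. Section 11.4 adds: "Any patient that discontinues from the study, regardless of the reason, will be requested to complete all Early Discontinuation visit assessments/procedures". The SGI is on that list.

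For rescued patients, SAP 2.3 says that "the observations collected at the time of rescue will be analyzed with the other Day 4 observations". SAP 4.2.1 lets the post-treatment value for any early discontinuation come from before Day 4, and makes the FAS the primary set.

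**The concern.** A fixed look-back of three days suits a visit at least three days after the treatment change. Early Discontinuation can come sooner. A patient who follows the printed instruction then rates a period spent partly on known, individually optimised open-label drug, and the analysis files the answer as a result of blinded treatment.

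The patients most exposed are those who deteriorate fastest. If they are mainly on placebo, their recorded fall is too small and the between-arm difference shrinks. With about 13 patients per arm, one or two such scores can matter to a co-primary endpoint. The wording cannot be repaired once the answers have been collected.

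**Working it through.** **1. Day count.**
- Day 0: at least 7 days of stable open-label dosing precede the rating, so the 3-day window is all open-label.
- Day 4: the visit is matched to the same dose of the day as Day 0, so it falls about 4 × 24 = 96 hours later. Dosing is three to four times a day, so the gap between the Day 0 assessments and the next dose is under 24 hours. More than 96 − 24 = 72 hours are on blinded tablets, and the window is all blinded.
- Early Discontinuation *h* hours after the first blinded dose, with *h* < 72: the open-label share is (72 − *h*)/72. At 24 hours it is 48/72 = 2/3; at 48 hours it is 24/72 = 1/3.

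**2. The plan's own power figure.** Protocol 13.1 and SAP 1.3 give an SGI difference of 2.1, SD at most 2, N = 26 and 80% power; the SAP specifies two-sided 0.05. With 13 per arm I get 76.3% by the normal approximation and 72.9% by the noncentral t. The stated 80% does not reproduce. That is a separate matter, but it is why the illustration starts at 73%.

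**3. Upper illustration.** Inputs: a placebo fall of 2.7 (LMS-002, Protocol 6.4.2). Assumptions that are not in the documents: the patient averages linearly over the window, rates open-label days as no change, is assessed at the stated hour, and the SD stays at 2.
- Recorded fall = 2.7 × *h*/72. At 24 hours: 2.7 × 1/3 = 0.9. At 48 hours: 2.7 × 2/3 = 1.8.
- Loss in the arm difference = (*r*/13) × (2.7 − recorded fall), where *r* placebo patients are affected.

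| Assessed at | *r* of 13 | Loss | Difference left | t-test power |
|---|---|---|---|---|
| – | 0 | 0 | 2.10 | 72.9% |
| 24 h | 1 | 1.8/13 = 0.14 | 1.96 | 67.0% |
| 24 h | 2 | 3.6/13 = 0.28 | 1.82 | 60.7% |
| 48 h | 1 | 0.9/13 = 0.07 | 2.03 | 70.0% |
| 48 h | 2 | 1.8/13 = 0.14 | 1.96 | 67.0% |

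**4. A milder scaling.** Apply the open-label share to the planned difference instead: 2.1 × (1 − (*r*/13) × 2/3). At 24 hours this gives 1.99 for *r* = 1 and 1.88 for *r* = 2, with power 68.3% and 63.5%.

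**5. Lower end.** If patients rate only their current state, or only the blinded tablets, the loss is 0.

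**6. Would a planned analysis reveal it?** The randomization test in SAP 4.2.1 permutes treatment labels over the same scores, so it cannot. The PP set (SAP 2.2) requires at least 80% of doses and at least 4 days enrolled, so it largely drops these patients rather than correcting their scores.

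**The case against.** **The item asks about the medication, not the days.** Sections 11.2 to 11.4 use study medication for the blinded tablets and call the earlier supply open-label. A patient could therefore rate the blinded tablets alone. This stands as a possible reading. But the same item rates open-label drug on Day 0, and no text supplied tells the patient to exclude earlier days. The wording is ambiguous, which is a reason to settle it. A reader might infer that rescued patients do rate open-label drug; the documents do not show that.

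**The Study Reference Manual may cover it.** Protocol 8.7.1 cites it for SGI instructions. It was not available, so this stays open.

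**Early rescue is not established.** A reader might infer it from the 1.8-hour half-life in Protocol 6.4.1. That figure comes from single doses in healthy men, and 6.4.1 reports 10-fold ranges in PK values. The documents give no rescue rate or day for this trial.

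**Linear averaging is doubtful.** From the LMS-002 on-drug mean of 5.9, a patient withdrawn at 24 hours for clinically significant worsening would score 5.9 − 0.9 = 5.0, still mostly satisfied on the scale. Many would mark lower. This stands, and it is why the figures are an upper illustration.

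**The PP analysis already sets these patients aside.** True, but the FAS is primary, and setting them aside loses their information.

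**A special early-visit wording would make the item depend on an outcome that differs by arm.** This stands, and it decides the form of the fix.

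**Conclusion.** The mismatch is real on the documents supplied. One fixed window serves Day 0 and Day 4 but not an Early Discontinuation visit under 72 hours from the switch, and that score enters the co-primary FAS analysis as if it were Day 4.

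If such visits fall mainly on placebo, the bias is toward no effect. A reader might suspect that it could favour the drug falsely. It cannot: with no true effect, early stopping, and so the dilution, is balanced in expectation. The risk is lost power and a less interpretable score.

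The size is unknown. It runs from zero to, under the stated assumptions, a loss of 0.14 or 0.28 points for 1 or 2 of 13 placebo patients assessed at 24 hours. A reader might extend the table to more rescues and much lower power, but nothing in the documents supports a particular count.

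The QMG is measured at the visit and is not affected. The most-bothersome-symptom Question 2 in Appendix 5 asks "how would you rate the most bothersome symptom that you previously identified, during the last 24 hours". It has a similar gap only for assessments within 24 hours of the switch, its opening refers to treatment with the study medication, and it is exploratory.

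**What to change.** In Appendix 2 and the source form, use one wording for every post-baseline SGI, at Day 4 and Early Discontinuation alike, for example: *the effects of the blinded study medication during the preceding 3 days, or since you started it if that is less than 3 days*. The meaning is unchanged for Day 4 completers, and the item stays the same for all patients. Bring any SGI text in the Study Reference Manual into line.

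The cost is one line in the appendix and the form. The downside is a shorter recall period for the few patients who stop early, set against a 3-day rating on Day 0. Limiting Question 2 of Appendix 5 in the same way is optional. An SAP flag for SGI scores taken under 72 hours from the first blinded dose would add little by itself.
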